### 16.3 Secondary Endpoints

The following endpoints will be compared between the 2 arms: best overall response, 6- month progression-free survival, changes in serum thyroglobulin levels, and adverse event rates between the 2 treatment arms. All patients who meet the eligibility criteria, sign the consent form, are randomized, and start any treatment will be considered evaluable for the endpoints below.

**Best overall response:** The best overall response will be compared between the two according to the criteria outlined in Section 11.0. This comparison will be done using a chi-square test. For a patient to be classified as a response, they need a partial or complete response that is confirmed at least 4 weeks later anytime during the study.

**Progression-Free Survival:** Progression-free survival (PFS) is defined as the time from study entry to the first of either disease progression or death from any cause, where disease progression will be determined based on criteria outlined in Section 11.0. PFS will be estimated using the Kaplan-Meier method, where the log-rank test will be used to compare the 2 treatment arms. Evidence of progression noted from the time of registration to within 6 months after  $^{131}\text{I}$  therapy may be disregarded as a progression event if the treating physician feels it is reasonable according to the rationale detailed in Section 16.2. The response assessment at 6 months for these patients will be based upon a comparison between the 6-month radiologic scan(s) and the baseline, pre-study radiologic scans. In addition, the 6-month PFS rate will also be compared between the arms.

**Serum Thyroglobulin Levels:** Changes in thyroglobulin will be assessed. The Wilcoxon Rank-Sum test will be used to compare the changes in thyroglobulin (pre-RAI and post-RAI) between the two treatment arms. (This analysis will not be possible for patients with detectable thyroglobulin antibodies.)

**Adverse events:** The maximum grade for each type of adverse event will be summarized using CTCAE version 4.0. The frequency and percentage of grade 3+ adverse events will be compared between the 2 treatment arms. Comparisons between arms will be made by using either the Chi-square or Fisher's Exact test.

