16. Adverse events for selumetinib will be monitored for up to 30 days after discontinuation of drug.
  
17. If an ongoing reduction in left ventricular ejection fraction of  $\geq 10\%$  and to below 55% at time of selumetinib or placebo discontinuation is noted, then a follow-up echocardiogram, single ECG, and vital sign assessment should be considered approximately 1 month after drug/placebo discontinuation.
18. For patients with non-measurable/non-target lesions and lymph nodes, serum TG measured in the context of TSH suppression (TSH  $\leq 0.4$  mcU/ml) will be used as part of disease response assessment. For the primary endpoint, serum TG must be assessed with TSH  $\leq 0.4$  mcU/ml at baseline (pre-treatment) and at the 6-month assessment of response (6 months s/p RAI). For all other measurements of serum TG in these patients, it is preferred that the TSH  $\leq 0.4$  mcU/ml, but it is not an absolute requirement. If the 6-month serum TG is initially measured in the context of a TSH  $>0.4$  mcU/ml, then every effort should be made to repeat this assessment until a serum TG value is obtained in the context of a TSH  $\leq 0.4$  mcU/ml, even if it requires obtaining the measurement outside of the protocol-defined +/- 1 week window. Serum TG values that have to be obtained outside this protocol-defined window to ensure it is measured in the context of TSH  $\leq 0.4$  mcU/ml will still be used for the primary assessment of response. **IMPORTANT:** Use of any thyroglobulin assay is allowed, though all serum thyroglobulin measurements for study purposes must be conducted with the same thyroglobulin assay. These requirements do not apply to patients with measurable disease.

R “Research funded” (see Section 19.0)

\*Note: ***Observation Phase:*** Part of the Active Monitoring Phase of a study. The time period following the active treatment phase when the participant continues to receive cycles of evaluation in compliance with the Test Schedule and may be required to return to the consenting site. Participants will be required to return to the consenting site for follow-up.

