## 10.4 Expedited Adverse Event Reporting Requirements for IND/IDE Agents

10.41 **Late Phase 2 and Phase 3 Studies:** Expedited Reporting via the **ACCRU Adverse Event Expedited Report Form** for Adverse Events That Occur Within 30 Days of the Last Dose of the Investigational Agent**FDA REPORTING REQUIREMENTS FOR SERIOUS ADVERSE EVENTS (21 CFR Part 312)**

**NOTE:** Investigators **MUST** immediately report to the sponsor **ANY** Serious Adverse Events, whether or not they are considered related to the investigational agent(s)/intervention (21 CFR 312.64)

An adverse event is considered serious if it results in **ANY** of the following outcomes:

- 1) Death
- 2) A life-threatening adverse event
- 3) An adverse event that results in inpatient hospitalization or prolongation of existing hospitalization for  $\geq$  24 hours
- 4) A persistent or significant incapacity or substantial disruption of the ability to conduct normal life functions
- 5) A congenital anomaly/birth defect.
- 6) Important Medical Events (IME) that may not result in death, be life threatening, or require hospitalization may be considered serious when, based upon medical judgment, they may jeopardize the patient or subject and may require medical or surgical intervention to prevent one of the outcomes listed in this definition. (FDA, 21 CFR 312.32; ICH E2A and ICH E6).

**ALL SERIOUS** adverse events that meet the above criteria **MUST** be immediately reported to the sponsor within the timeframes detailed in the table below.

Hospitalization	Grade 1 Timeframes	Grade 2 Timeframes	Grade 3 Timeframes	Grade 4 & 5 Timeframes
Resulting in Hospitalization $\geq$ 24 hrs	7 Calendar Days			24-Hour; 3 Calendar Days
Not resulting in Hospitalization $\geq$ 24 hrs	Not required		7 Calendar Days	

**NOTE** Protocol specific exceptions to expedited reporting of serious adverse events are found in section 10.31 of the protocol.

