## **13.0 Treatment/Follow-up Decision at Evaluation of Patient**

13.1 Patients who are CR, PR, or SD will continue treatment/assessment per protocol. Patients that are non-PD after completing treatment will be followed during the observation phase as outlined in Section 4.0: 1 month post-treatment, 3 months post-treatment, followed by every 3 months until 12 months post-treatment when patients will be followed every 6 months for a maximum of 2 years (+/- 3 months) from randomization.

13.2 Patients who develop PD while receiving therapy or undergoing protocol assessment will be followed in the event monitoring phase (see section 18). However, it is possible that patients will have PD early in the study and still demonstrate benefit from the study treatment later in the study for several reasons: 1) selumetinib alone prior to RAI may not have significant clinical efficacy, 2) Thyrogen™ stimulation can transiently increase tumor size which can be mistaken for disease progression; 3) the therapeutic effects of RAI can be delayed; and 4) evidence of progression may be evident prior to administration of RAI. Hence, patients with evidence of radiographic, clinical or biochemical (i.e. thyroglobulin, if applicable) PD noted prior to the 6-month disease evaluation (i.e. the scans and evaluations performed 6 months after therapeutic  $^{131}\text{I}$  is administered) may remain on treatment/assessment at the discretion of the treating physician. If, in the opinion of the treating physician, these patients are unlikely to demonstrate benefit with subsequent clinical assessments, the patients will be classified as having PD and will be followed in the event monitoring phase (see Section 18.0).

13.3 Patients who go off protocol treatment for reasons other than PD will go to the event-monitoring phase per Section 18.0.

13.4 Patients who develop CNS PD at any time should go to event monitoring. These patients should receive treatment if deemed clinically indicated by the treating physician(s).

13.5a A patient is deemed ineligible if after registration, it is determined that at the time of registration, the patient did not satisfy each and every eligibility criteria for study entry. The patient may continue treatment off-protocol at the discretion of the physician as long as there are no safety concerns, and the patient was properly registered. The patient will go directly to the event-monitoring phase of the study (or off study, if applicable).

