- If the patient received treatment, all data up until the point of confirmation of ineligibility must be submitted. Event monitoring will be required per Section 18.0 of the protocol.
- If the patient never received treatment, on-study material must be submitted. Event monitoring will be required per Section 18.0 of the protocol.

13.5b A patient is deemed a major violation, if protocol requirements regarding treatment in cycle 1 of the initial therapy are severely violated such that evaluation of the primary end point is significantly compromised. All data up until the point of confirmation of a major violation must be submitted. The patient will go directly to the event-monitoring phase of the study. The patient may continue treatment off-protocol at the discretion of the physician as long as there are no safety concerns, and the patient was properly registered. Event monitoring will be required per Section 18.0 of the protocol.

13.5c A patient is deemed a cancel if he/she is removed from the study for any reason before any study treatment is given. On-study material and the End of Active Treatment/Cancel Notification Form must be submitted. No further data submission is necessary.

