#### 16.8 Data & Safety Monitoring

The principal investigator(s) and the study statistician will review the study at least twice a year to identify accrual, adverse event, and any endpoint problems that might be developing. The trial is monitored continually by the study team who are notified of every grade 4 and 5 event in real time. The Mayo Clinic Cancer Center (MCCC) Data Safety Monitoring Board (DSMB) is responsible for reviewing accrual and safety data for this trial at least twice a year, based on reports provided by the MCCC Statistical Office.

The stopping rule specified below is based on the knowledge available at study development. We note that the Adverse Event Stopping Rule may be adjusted in the event of either (1) the study re-opening to accrual after any temporary suspension or (2) at any time during the conduct of the trial and in consideration of newly acquired information regarding the adverse event profile of the treatment(s) under investigation. The study team may also choose to suspend accrual because of unexpected adverse event profiles that have not crossed the specified rule below.

Accrual will be temporarily suspended to this study if at any time we observe events considered at least possibly related to study treatment (i.e., an adverse event with attribute specified as "possible", "probable", or "definite") that satisfy any of the following criteria for each arm separately:

- If at any time, 6 of the initial 20 treated patients or 30% or more of all patients (i.e. when accrual is greater than 20 patients) have experienced a grade 4 non-hematologic adverse event.
- If at any time, 2 of the initial 20 treated patients or 10% or more of all patients (i.e. when accrual is greater than 20 patients) have experienced a grade 5 adverse event (non-progressive disease).
- In addition, each grade 5 event will be reviewed on a case by case basis in a real time fashion to determine whether study accrual should be suspended. We may suspend accrual after just 1 grade 5 AE, if needed, for patient safety.

16.9a Accrual Monitoring Stopping Rule

Given the expected accrual rate is around 4 patients per month, it is expected that the study will take around 25 months to fully accrue. We plan to monitor the accrual continually and if we only end up accruing 10 patients or less in the first year (after study activation), we will consider stopping the trial for slow accrual.

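### Section 16.3 restricts the grade 3+ adverse-event comparison to eligible patients, and the data cut-offs in 13.5a and 13.5b conflict with the adverse-event collection rules in 10.52 and footnote 16

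*Combined protocol and SAP*

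**What the plan says.** **Analysis population.** Section 16.3 names adverse event rates among the secondary endpoints and then defines who is counted: "All patients who meet the eligibility criteria, sign the consent form, are randomized, and start any treatment will be considered evaluable for the endpoints below". The adverse-event paragraph comes under that sentence and states: "The frequency and percentage of grade 3+ adverse events will be compared between the 2 treatment arms". Neither 16.3 nor any other section defines a separate safety population.

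**Late ineligibility.** Section 13.5a allows the finding to come when a patient is already on the trial, if "it is determined that at the time of registration, the patient did not satisfy each and every eligibility criteria for study entry". Treatment need not end: "The patient may continue treatment off-protocol at the discretion of the physician as long as there are no safety concerns". The patient moves to event monitoring, and the data duty is limited: "If the patient received treatment, all data up until the point of confirmation of ineligibility must be submitted". Section 13.5b sets the same kind of cut-off, at confirmation, for major violations. Patients removed before any treatment are a separate class, cancellations (13.5c).

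**Adverse-event collection.** Footnote 16 of the test schedule (4.0) reads: "Adverse events for selumetinib will be monitored for up to 30 days after discontinuation of drug". Section 10.52 asks for case report forms on grade 3 and 4 events whatever their cause, on treatment-related grade 2 events and on deaths, with no eligibility condition. Expedited reporting in 10.4 covers all serious events "whether or not they are considered related to the investigational agent(s)/intervention".

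**Monitoring.** The first suspension criterion in 16.8 is applied to each arm and counts "6 of the initial 20 treated patients or 30% or more of all patients", again without reference to eligibility.

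**The concern.** Safety and tolerability is a stated objective (2.24). A toxicity comparison is normally made in everyone exposed, because whether a patient met the entry criteria has no bearing on whether the drug caused an event. Here a finding made after treatment has begun takes an exposed patient out of both the numerator and the denominator.

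The finding need not be independent of toxicity. Some exclusion criteria in 3.27 and 3.28 (low ejection fraction, uncontrolled hypertension, raised intra-ocular pressure, past retinal disease) concern organs that selumetinib is known to affect. Work-up of an on-treatment event could uncover a disqualifying history.

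There is also a conflict over data. A site reading 13.5a or 13.5b may stop sending adverse-event forms at confirmation. A site reading 10.52 and footnote 16 would continue. Event counts would then depend on which section the site followed.

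**Working it through.** **1. The plan's own figures.** The plan gives no figure for the adverse-event comparison, so the relevant ones are the denominators.

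- Evaluable number (16.2): 40% versus 65%, one-sided 0.15, power 80%. With mean rate 0.525, n = [1.036·√(2·0.525·0.475) + 0.842·√(0.40·0.60 + 0.65·0.35)]² / 0.25² = (0.732 + 0.575)² / 0.0625 ≈ 27.3, so 28 per arm. This reproduces the plan.
- Accrual (16.5): 56 × 1.05 = 58.8, or 59. The plan states 60, 30 per arm.
- Gap between accrued and evaluable: 60 − 56 = 4 patients, 4/60 = 6.7%.

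The 4 places also cover cancellations, who are untreated, as well as major violations and other reasons. The number treated but ineligible is not given. The assumed range is 0 to 4.

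**2. Effect on one arm's rate.** Let n patients be treated, x of them with a grade 3+ event. Let k be excluded as ineligible, e of those with an event. The all-treated rate is x/n and the reported rate is (x − e)/(n − k). The reported rate is lower than the all-treated rate exactly when e/k > x/n, and higher when e/k < x/n.

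Take n = 30 and k = 2 (assumed counts):

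| All treated | Both excluded had an event | Neither did |
|---|---|---|
| 3/30 = 10.0% | 1/28 = 3.6% | 3/28 = 10.7% |
| 6/30 = 20.0% | 4/28 = 14.3% | 6/28 = 21.4% |
| 9/30 = 30.0% | 7/28 = 25.0% | 9/28 = 32.1% |

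In the middle row, one event among the two gives 5/28 = 17.9%. The error over these rows runs from about 6 points too low to about 2 points too high.

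**3. The collection rules side by side.**

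| Provision | Eligibility condition? | When it ends |
|---|---|---|
| 16.3 comparison | Yes | Not stated |
| 13.5a, treated ineligible | Applies to ineligible patients | Confirmation of ineligibility |
| 13.5b, major violation | None | Confirmation of violation |
| 10.52 case report forms | None | Not tied to confirmation |
| Footnote 16 | None | Up to 30 days after stopping drug |
| 10.4 and 10.312, serious events and deaths | None | 30 days after last dose; later if attributed |
| 16.8 stopping rule | None | Not stated |

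Section 18.1 adds to the conflict. The Nadir/Adverse Event form is listed only for the active-monitoring phase. The event-monitoring phase, to which 13.5a and 13.5b send the patient, lists one form, scheduled around progression, death and new primaries.

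**4. What expedited reporting does not cover.** It concerns serious events, and 10.31 exempts many expected ones up to grade 3 when there is no hospitalisation, among them rash, diarrhoea, fatigue, blurred vision, hypertension and raised transaminases. Grade 3 events of that kind count in the 16.3 comparison and may be recorded only on the routine form.

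**The case against.** The strongest case against is that little is lost. Serious events and deaths are reported regardless of eligibility. Section 10.52 asks for grade 3 to 5 events on case report forms. The study team hears of every grade 4 and 5 event as it occurs, and the monitoring board reviews safety at least twice a year. Data from before confirmation are still submitted. Section 10.53 refers to a forms packet for late events after active monitoring, and that packet may give further instructions. Echocardiography, blood pressure and eye examination are all done before registration, and the registration application checks eligibility, so late ineligibility may well concern scan dates or contrast timing, which have no link to toxicity. A stopping rule that covers all treated patients is the more protective choice, so its difference from 16.3 is not an error in itself.

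Most of this stands, and it rules out two stronger readings that a reader might infer. The first is that toxicity in these patients disappears from the trial. The provisions just listed show that it does not. The second is that the comparison must understate selumetinib toxicity. Exclusion removes patients from numerator and denominator together, and the reported rate falls only if the excluded patients had a higher event rate than the arm as a whole. The documents give no reason to be sure of that.

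What the objection leaves untouched is that none of these provisions makes a treated ineligible patient evaluable under 16.3, or says whether 13.5a and 13.5b override 10.52 and footnote 16.

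**Conclusion.** The point holds in limited form. As written, the grade 3+ comparison omits any patient who took study drug and was later found ineligible, and the cut-offs in 13.5a and 13.5b cannot be squared with 10.52 and footnote 16.

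The size is small and uncertain. It rests on an assumed 0 to 4 patients of 60 and, for the worked example, 2 excluded from one arm of 30. On those assumptions a 20.0% rate could read anywhere from 14.3% to 21.4%. The direction is not determined by the documents. The primary endpoint, the sample size and the stopping rule are unaffected. It is still worth correcting, because with about 30 patients per arm one event is worth 1/30 = 3.3 percentage points and safety is a named objective.

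**What to change.** 1. In 16.3, limit the eligibility condition to the efficacy endpoints. State that adverse events are summarised and compared in all randomised patients who took at least one dose of selumetinib or placebo, by treatment received and regardless of eligibility.

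2. In 13.5a and 13.5b, reconcile the data cut-off with 10.52 and footnote 16, so that adverse-event forms are submitted through 30 days after the last dose of study drug for every treated patient. Align the form schedule in 18.1. Flag events that occur after confirmation so that they can be listed separately.

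Both changes are needed. Widening the population alone would bring these patients into the denominator with their event data cut short.

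The cost is a few wording changes and adverse-event forms for a handful of patients. The denominator rises from 28 to at most 30 per arm. The reported toxicity rate may turn out somewhat less favourable.

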**11.432 Evaluation of Target Lesions**

- Complete Response (CR): All of the following must be true:
  - a. Disappearance of all target lesions.
  - b. Each target lymph node must have reduction in short axis to <1.0 cm (if short axis being used for measurement) or have reduction in long axis to < 0.7 cm (if long axis is being used for measurement).
  - c. For patients without detectable thyroglobulin antibodies, serum thyroglobulin on suppression must be measured to be <0.2 ng/ml. If a center does not have a thyroglobulin assay that reads to <2 ng/ml, then a TSH-stimulated Tg <1 ng/ml would be required to confirm complete response. For patients with detectable thyroglobulin antibodies, assessment of thyroglobulin will not be necessary for assessment of complete response.
- Partial Response (PR): At least a 30% decrease in PBSD (sum of the longest diameter for all target lesions plus the sum of the long or short axis of all the target lymph nodes (depending on which axis is being used for assessments) at current evaluation) taking as reference the BSD (see Section 11.41).
- Progression (PD): At least one of the following must be true:
  - a. At least one new malignant lesion, which also includes any lymph node that was normal at baseline (<1.0 cm short axis) and increased to  $\geq 1.0$  cm short axis and is deemed to be malignant during follow-up.
  - b. At least a 20% increase in PBSD (sum of the longest diameter for all target lesions plus the sum of the long or short axis of all the target lymph nodes (depending on which axis is being used for assessments) at current evaluation) taking as reference the MSD (Section 11.41). In addition, the PBSD must also demonstrate an absolute increase of at least 0.5 cm from the MSD.

- c. See Section 11.32 for details in regards to the requirements for PD via FDG-PET imaging.
- Stable Disease (SD): Neither sufficient shrinkage to qualify for PR, nor sufficient increase to qualify for PD taking as reference the MSD.

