#### **Overall Objective Status for Patients with Non-Measurable, Non-Target Lesions/Lymph nodes**

The overall objective status for an evaluation is determined by:

- Structural assessment of lesions/lymph nodes as detailed in Section 11.442.
- For the “non-CR/non-PD” structural category, measurement of the serum TG in the context of suppressed TSH (and negative TG antibody) will be used to determine the final response designation (the exception is for the assessment of complete response, which requires measurement of a stimulated TG, see chart below).

Non-Target Lesions & Non-Target Lymph Nodes	Serum Thyroglobulin (TG)* (or TG antibody)	New Sites of Disease	Overall Objective Status
CR	TG < 0.2 ng/ml on TSH suppression* OR stimulated TG < 0.1 ng/ml (see 11.442)	No	CR
CR	TG ≥ 0.2 ng/ml on TSH suppression* OR stimulated TG > 0.1 ng/ml (see 11.442)	No	Assess as per Non-CR/Non-PD
Non-CR/Non-PD	50% or more reduction compared to baseline Tg WITHOUT a 25% or more increase compared to the lowest TG measured on study (baseline or nadir)*	No	PR
Non-CR/Non-PD	25% or more increase compared to the lowest TG measured on study* (baseline or nadir)	No	PD
Non-CR/Non-PD	Less than 50% reduction compared to baseline TG WITHOUT a 25% or more increase compared to the lowest TG measured on study* (baseline or nadir)	No	SD
Non-CR/Non-PD	New detection of TG antibody	No	PD
Not All Evaluated	25% or more increase compared to lowest TG measured on study Tg* (baseline or nadir)	No	PD

Non-Target Lesions & Non-Target Lymph Nodes	Serum Thyroglobulin (TG)* (or TG antibody)	New Sites of Disease	Overall Objective Status
Not All Evaluated	WITHOUT 25% or more increase compared to lowest TG measured on study Tg* (baseline or nadir)	No	NE
Uequivocal PD	Any serum TG result or TG antibody result, including failure to complete the measurement as per protocol	Yes or No	PD
CR Non-CR/Non-PD Not All Evaluated	Any serum TG or TG antibody result, including failure to complete the measurement as per protocol	Yes	PD
CR Non-CR/Non-PD Not All Evaluated	TG was not evaluated or not evaluated in the context of TSH suppression*	No	NE

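### The thyroglobulin comparison fixes neither scale nor visit and is unstratified, while TSH-suppression and same-assay rules are waived for measurable disease: mainly lost precision

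*Combined protocol and SAP*

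**What the plan says.** Comparing thyroglobulin change between arms is a named secondary objective (Section 2.2, goal 2.23). The analysis is one sentence in Section 16.3: "The Wilcoxon Rank-Sum test will be used to compare the changes in thyroglobulin (pre-RAI and post-RAI) between the two treatment arms". The population is all eligible, consented, randomised patients who "start any treatment will be considered evaluable for the endpoints below", with one exception: "This analysis will not be possible for patients with detectable thyroglobulin antibodies". Both disease groups are therefore pooled.

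The measurement rules are in Section 4.0, footnote 18. For non-measurable disease, TSH must be at or below 0.4 mcU/ml at baseline and at 6 months. At other visits suppression is optional: "For all other measurements of serum TG in these patients, it is preferred that the TSH" meets that limit. The footnote adds that "all serum thyroglobulin measurements for study purposes must be conducted with the same thyroglobulin assay", and then closes with "These requirements do not apply to patients with measurable disease". The only other same-assay statement is under criterion 3.16, which also covers non-measurable disease alone.

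Two response sections depend on TSH state. Section 11.432 requires, for a complete response in antibody-negative patients with target lesions, that "serum thyroglobulin on suppression must be measured to be <0.2 ng/ml", with a TSH-stimulated alternative for less sensitive assays. In the Section 11.443 table, when there are no new sites, the entry "TG was not evaluated or not evaluated in the context of TSH suppression" leads to a status of not evaluated.

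Section 16.1 expects 40% of patients to have measurable disease. Section 5.0 makes measurable disease a stratification factor.

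**The concern.** For non-measurable disease the protocol treats TSH state as essential to interpreting thyroglobulin. It makes the 6-month sample repeatable outside its window and refuses to score an unsuppressed value. The between-arm comparison then mixes those values with values from patients who have no such control, and the analysis does not separate the two groups.

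The test is also under-defined. Change could be absolute, percent or log. The Test Schedule collects thyroglobulin at 1, 3, 6, 9 and 12 months after radioiodine and six-monthly thereafter, so several different analyses fit the sentence. At stake are the power of a named secondary objective and the ability to say in advance which result is the planned one.

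**Working it through.** **The plan's own figure.** The documents give no power, alpha, effect or SD for thyroglobulin. The 28 per arm belongs to the primary endpoint and reproduces: [1.0364·√(2·0.525·0.475) + 0.8416·√(0.40·0.60 + 0.65·0.35)]² / 0.25² = 27.4, rounded up to 28. It does not bear on this point.

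**Patients without TSH or assay control.** 0.40 × 56 = 22.4, so about 22 patients before antibody exclusions.

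**Patients analysed per arm.** Criterion 3.16 requires undetectable antibody in non-measurable disease, so baseline antibody exclusions can fall only on measurable patients. Per arm, 0.40 × 28 ≈ 11 are measurable and 17 are not. Assuming 20% of the measurable are antibody-positive removes about 2, leaving 9 + 17 = 26.

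**Assumed model (none of these values is in the documents).** Log baseline SD 1.8; slope of log post on log baseline 0.85; residual SD 0.9; mean log change −0.5 on placebo and −1.2 on selumetinib. The effect is 0.7 log units, or a ratio of exp(−0.7) ≈ 0.50. The test is one-sided at 5%. In the noisy setting, an independent error of log-SD 0.7 is added to each sample from a measurable patient.

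**Analyses compared.**
- Raw: Wilcoxon on Tg(post) − Tg(baseline).
- Log ratio: Wilcoxon on log[Tg(post)/Tg(baseline)]. Percent change gives the same ranks, hence the same test.
- ANCOVA: log Tg(post) on arm, log Tg(baseline) and measurable-disease stratum.

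| Power | Raw | Log ratio | ANCOVA |
|---|---|---|---|
| No extra noise | 40% | 84% | 87% |
| Extra log-SD 0.7, measurable patients | 38% | 74% | 78% |

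Repeat simulations agree within about 2 points. Rejection rates with no true effect are about 4–6%.

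**Why the pattern arises.** Raw change equals baseline × (ratio − 1), so its ranks are driven largely by baseline level. On the log scale the variance of change is (0.15 × 1.8)² + 0.9² = 0.073 + 0.810 = 0.883. Baseline explains only 0.073 of this (8%), which is why adjusting for it adds little. The noise adds 2 × 0.7² = 0.98 for a measurable patient, giving 1.863, or 2.1 times the variance.

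**Range under other assumptions.** With 28 per arm, two-sided 5%, baseline log-SD 1.5, SD of log change 1.0, effect 0.7 and 40% measurable:

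| Noise log-SD | Raw | Log ratio | ANCOVA |
|---|---|---|---|
| 0 | 37% | 71% | 72% |
| 0.5 | 31% | 61% | 63% |
| 1.0 | 26% | 50% | 49% |
| 1.5 | 23% | 40% | 36% |

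Rejection rates with no true effect are about 4–5%. The gap between raw and log persists in every row. The small advantage of ANCOVA does not.

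**The case against.** The case for leaving the plan alone is substantial.

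- **A reader might infer bias.** The documents do not support that. Treatment is double-blind, allocation is balanced on measurable disease, and the simulations keep the nominal error rate.
- **A reader might infer that the planned test has only about 40% power.** That holds only if change means raw ng/ml, which Section 16.3 does not say. The thyroglobulin changes defined in Section 11.443 are percentages, and a Wilcoxon test on percent change is the log-ratio test. What stands is that the scale is unstated.
- **A reader might see missing baseline adjustment as the main defect.** A change score already uses baseline, and on the log scale ANCOVA gains a few points at most.
- **A reader might see Section 11.432 as contradicting footnote 18.** It does not. Thyroglobulin enters there only to designate a complete response, and a stimulated alternative exists. Waiving routine suppression is compatible with that, though the sections should refer to each other.
- **A reader might infer that unsuppressed visits remove confirmation and progression detection in non-measurable disease.** New lesions and unequivocal structural progression count whatever the thyroglobulin result, the 6-month value must be suppressed, and confirmation may come at any time during the study. Only thyroglobulin-dependent calls at other visits are exposed.
- **The 5% level is not the trial's.** The only stated alpha is one-sided 0.15, for the primary endpoint. At 0.15 the noisy log-ratio Wilcoxon has about 88% power. The endpoint is secondary and no power is claimed for it.

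The same-assay sentence could also be read as covering everyone. However, the waiver follows it directly and is not limited to TSH, so the text needs to say which is meant.

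**Conclusion.** The concern holds as one of definition and precision. Section 16.3 pools evaluable antibody-negative patients from both disease groups in an unstratified test with no scale and no visit, while about 40% of the evaluable sample is expected to be exempt from the TSH and same-assay rules. The choice of scale matters most: about 40% against 84% power under the main assumptions. Extra variation in measurable patients costs about 10 points on the log scale (84% to 74%) if its log-SD is 0.7, and more if it is larger. Baseline adjustment is a minor gain.

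All power figures rest on assumed spreads, effect, noise and antibody prevalence. The documents supply only the 28 per arm, the 40% and the confinement of baseline antibody exclusions to measurable disease. The finding does not affect the primary sample size and does not show a biased comparison. It merits a change because the remedy is cheap and removes the choice among several analyses.

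**What to change.** In Section 16.3, define the endpoint as log(6-month/baseline thyroglobulin) in evaluable patients without detectable antibodies. Analyse it by ANCOVA with arm, log baseline and the measurable-disease stratum, or by a van Elteren test stratified by measurable disease. Add a rule for values below the assay limit, since the log scale needs one.

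Apply the one-assay-per-patient rule to everyone in this analysis and record the assay. Add a sensitivity analysis limited to same-assay pairs with TSH at or below 0.4 mcU/ml at both times; the Test Schedule already draws TSH with each thyroglobulin.

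Reconcile footnote 18 with Sections 11.432, 11.443 and 16.3, so that the optional suppression at other visits and the waiver for measurable disease are stated consistently with how those values are used. This is a matter of consistency and does not call for a TSH management rule.

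The cost is some SAP and footnote wording, slightly more analysis and one more recorded field.
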